11.3 General

It is expected that patients with nausea, emesis, diarrhea, or constipation will receive appropriate medical management without dose modification. However, patients with persistent (≥ 24 hours) Grade ≥ 3 toxicity in spite of optimal medical management require reduction of one dose level and delay in subsequent therapy for a maximum of 2 weeks until recovered to Grade 1.

Other non-hematologic toxicities with an impact on organ function of Grade ≥ 2 require delay in subsequent therapy for a maximum of 28 days until recovered to Grade 1, or pre-therapy baseline.

Hematopoietic Growth Factors and Blood Products

Erythropoietin, darbepoetin alfa, romiplostim and/or hematopoietic colony-stimulating factors for treatment of cytopenias should be administered according to institutional guidelines. Transfusion thresholds for blood product support will be in accordance with institutional guidelines.

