9.1 TREATMENT/INTERVENTION PLAN

All subjects will be randomized to one of two treatment arms in a 1:1 fashion.

Arm 1: Patients will receive intravenous (IV) infusion of durvalumab 1500mg Fixed Dose every 4 weeks until patient develops a loss of clinical benefit or experiences unacceptable toxicities.

Arm 2: Patients will receive durvalumab + tremelimumab combination therapy. Patients will receive 1500 mg Fixed Dose durvalumab via IV infusion q4w for up to 4 cycles and 75 mg tremelimumab via IV infusion q4w for up to 4 cycles, and then continue 1500 mg Fixed Dose durvalumab every 4 weeks until patient develops a loss of clinical benefit or experiences unacceptable toxicities.

Date:

Dosing outside the window should be discussed with the Principal Investigator. Tremelimumab will be administered first. Durvalumab infusion will start approximately 1 hour after the end of tremelimumab infusion. The duration will be approximately 1 hour for each infusion. A 1-hour observation period is required after the first infusion of single agent durvalumab and combination durvalumab and tremelimumab. If no clinically significant infusion reactions are observed during or after the first cycle, subsequent infusion observation periods can be at the Investigator's discretion (suggested 30 minutes after each durvalumab single agent infusion 30 minutes after the combination durvalumab and tremelimumab infusion).

1. Patients will receive study treatment until disease progression, intolerable toxicity, elective withdrawal from the study, study completion, or study termination.
2. Radiologic tumor assessment will be repeated every 8 weeks +/- 7 days for the first 48 weeks and then every 12 weeks +/- 7 days until PD. For patients who remain progression free 2 years post completion of protocol directed treatment, every 6 months +/- 1 month.
3. Safety will be evaluated in this study through the monitoring of all serious and non-serious AEs and irAEs, graded according to the current version of the National Cancer Institute Common Terminology Criteria for Adverse Events. Procedures to be conducted during the treatment phase of the study are presented in the Schedule of Assessments (Section 10.0).
4. Pre- and post-treatment blood and serum samples, as well as archival tumor tissue (when available) will be collected for biomarker analysis (as per Appendix E).

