11.1 TOXICITIES/SIDE EFFECTS

The dose delay and reduction instructions provided in this section are intended to serve as guidelines to allow ongoing treatment for patients experiencing clinical benefit without signs or symptoms of progression while ensuring patient safety. Patients may temporarily suspend dosing of study drug for up to 14 days if they experience toxicity that is considered related to study drug and requires that a dose be held. Patients who miss ≥ 28 consecutive days of scheduled study treatment because of drug-related AEs will be discontinued from the study. Exceptions may be made after discussion with and approval by the Principal Investigator.

Patients may suspend dosing of study drug for radiation therapy or surgery that is considered by the treating physicians to be of clinical benefit for the patient. After completion of the intervention, patients may restart the study drug as long as all criteria for dosing are met and there is no evidence of disease progression (unless approved by PI and sponsor as noted previously).

For adverse events (AEs) that are considered at least partly due to administration of durvalumab or tremelimumab the following dose adjustment guidance may be applied:

Date:

- Treat each of the toxicities with maximum supportive care (including holding the agent suspected of causing the toxicity where required).
- If the symptoms promptly resolve with supportive care, consideration should be given to continuing the same dose of durvalumab or tremelimumab along with appropriate continuing supportive care.
- In addition, there are certain circumstances in which durvalumab or tremelimumab should be permanently discontinued.

Following the first dose of durvalumab or tremelimumab, subsequent administration of durvalumab or tremelimumab can be modified based on toxicities observed (see Table 4). Dose reductions are not permitted

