Based on the mechanism of action of durvalumab or tremelimumab leading to T-cell activation and proliferation, there is the possibility of observing immune related Adverse Events (irAEs) during the conduct of this study. Potential irAEs include immune-mediated colitis, pneumonitis, hepatitis/hepatotoxicity, neuropathy/neuromuscular toxicity, endocrinopathy, dermatitis, pancreatitis and nephritis. Subjects should be monitored for signs and symptoms of irAEs. In the absence of an alternate etiology (e.g., infection or PD) signs or symptoms of colitis, pneumonitis, hepatitis/hepatotoxicity, neuropathy/neuromuscular toxicity, endocrinopathy, dermatitis, pancreatitis and nephritis should be considered to be immune-related.

Dose modification recommendations and toxicity management guidelines for immune-mediated reactions, for infusion-related reactions, and for non-immune-mediated reactions are detailed in Tables 5 and 6.

In addition, management guidelines for adverse events of special interest (AESIs) are detailed in Section 11.4.3. All toxicities will be graded according to NCI CTCAE v4.03.

For patients who are being treated with both durvalumab and tremelimumab, both agents will be held/discontinued in the event of a toxicity as described in Tables 4-6.

TABLE 4:

Date:

Dosing Modification and Toxicity Management Guidelines for Immune-mediated, Infusion Related, and Non Immune-mediated Reactions (MEDI4736 Monotherapy or Combination therapy with Tremelimumab or Tremelimumab Monotherapy) 28 October 2021 Version	
Immune-Mediated Reactions	
Dose Modifications	Toxicity Management

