	
Grade 3 or 4 (Grade 3 Diarrhea: stool frequency of ≥7 over baseline per day; Grade 4 Diarrhea: life threatening consequences) (Grade 3 Colitis: severe abdominal pain, change in bowel habits, medi-cal intervention indicated, peritoneal signs; Grade 4 Colitis: life-threatening consequences, urgent intervention indicated) (Grade 3 Perforation: severe symptoms, elective* operative intervention indicated; Grade 4 Perforation: life-threatening consequences, urgent intervention indicated) *This guidance anticipates that Grade 3 operative interventions of perforations are usually not elective
	
Grade 3
 
 – For patients treatet with durvalumab monotherapy, hold study drug/study regimen until resolution to Grade ≤1; study drug/study regimen can be resumed after completion of steroid taper (<10 mg prednisone per day, or equivalent). – For patients treated with durvalumab in combination with other products (not tremelimumab), decision to be made at the discretion of the study investigator, in discussion with AstraZeneca Clinical Study Lead. – For p atient s t reat ed with durvalumab in combination with tremelimumab or tremelimumab monotherapy. Permanently discontinue study drug for 1) Grade 3 diarrhea colitis or 2) Any grade large intestine perforation in any patient treated with immune checkpoint inhibitor (ICI). 	
For Grade 3 or 4:
 
 – Promptly initiate empiric IV methylprednisolone 1 to 2 mg/kg/day or equivalent. – Monitor stool frequency and volume and maintain hydration. – Urgent GI consult and imaging and/or colonoscopy as appropriate. – If still no improvement within 2 days continue steroids and promptly add further immunosuppressant agents (e.g., infliximab at 5 mg/kg IV, may be repeated at 2 and 6 weeks after initial dose at the discretion of the treating provider or relevant practice guidelines). Caution: Ensure GI consult to rule out bowel perforation and refer to infliximab label for general guidance before using infliximab. If perforation is suspected, consult a surgeon experienced in abdominal surgery immediately without any delay.

Date:

		
Grade 4
 
 – Permanently discontinue study drug/study regimen. 	

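### Section 11.3 orders a one-level dose reduction for persistent Grade 3 or worse gastrointestinal toxicity, although Section 11.1 bans reductions, no lower level exists, and Tables 4 and 6 say otherwise

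*Combined protocol and SAP*

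**What the plan says.** Section 11.3 (General) covers nausea, emesis, diarrhea and constipation. These are managed medically without dose modification unless Grade 3 or worse toxicity lasts at least 24 hours despite optimal management. Such patients "require reduction of one dose level and delay in subsequent therapy for a maximum of 2 weeks until recovered to Grade 1".

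Section 11.1 points to Table 4 for changes after the first dose of either drug and adds "Dose reductions are not permitted". Yet the same section opens with "The dose delay and reduction instructions provided in this section are intended to serve as guidelines".

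The treatment plan (Section 9.1) gives durvalumab alone at 1500 mg every 4 weeks in Arm 1. In Arm 2 it gives "1500 mg Fixed Dose durvalumab via IV infusion q4w for up to 4 cycles and 75 mg tremelimumab via IV infusion q4w". No reduced level of either drug is defined.

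Table 4, whose title covers "MEDI4736 Monotherapy or Combination therapy with Tremelimumab or Tremelimumab Monotherapy", handles diarrhea/colitis by grade and arm:

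- Grade 3 on the combination: "Permanently discontinue study drug for 1) Grade 3 diarrhea colitis".
- Grade 3 on durvalumab alone: hold to Grade 1 or lower, after which "study drug/study regimen can be resumed after completion of steroid taper (<10 mg prednisone per day, or equivalent)".
- Grade 4 in either arm: "Permanently discontinue study drug/study regimen".

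Table 6 (non-immune-mediated reactions) holds treatment at Grade 3. It allows resumption if the event falls to Grade 2 or lower within 7 days, or to Grade 1 or baseline within 14 days, and otherwise discontinues. At Grade 4 it discontinues, with a judgment clause for laboratory values only.

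**The concern.** A safety rule worded as a requirement is forbidden by one section and cannot be carried out under another. The trouble is not limited to the word reduction. The rule covers Grade 3 and above, so it includes Grade 4, and it assumes that dosing will resume. For a combination patient with Grade 3 diarrhea, one page says delay and re-treat while another says stop permanently. Section 11.4.3 describes diarrhea/colitis as the most common treatment-emergent SAE with tremelimumab monotherapy and notes rare perforation and fatal outcomes, so its stopping rule should be unambiguous.

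Dosing at a reduced level is unlikely, because staff would have to ask what the lower level is. The realistic stakes are an avoidable query, a plan to re-treat where a table says stop, and a possible deviation from one section whichever is followed.

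**Working it through.** **Comparing the instructions.** The plan states no figure to reproduce, so the check sets the text of Section 11.3 against each rule that covers the same patient.

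| Situation | Section 11.3 | Other rule | Agreement |
|---|---|---|---|
| Any qualifying event | Reduce one level | Section 11.1: no reductions; Section 9.1: one fixed dose per drug | None |
| Grade 3 diarrhea/colitis, combination | Delay up to 2 weeks, reduce, resume at Grade 1 | Table 4: stop permanently | None |
| Grade 3 diarrhea/colitis, durvalumab alone | Same | Table 4: hold, resume after steroid taper, full dose, no 2-week cap | Partial (both resume) |
| Grade 4 diarrhea/colitis, either arm | Same | Table 4: stop permanently | None |
| Grade 3 non-immune event | Same | Table 6: hold, resume on the 7-day or 14-day criterion, full dose | Delay window agrees; reduction and recovery grade do not |
| Grade 4 non-immune event | Same | Table 6: discontinue | None |

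Three provisions might be mistaken for a lower dose level, but none is one: weight-based dosing for patients at or below 30 kg (Section 3.0), the 750 mg every-2-weeks equivalent (Section 5.2), and the 50% cut in infusion rate after an infusion reaction.

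**Sizing Arm 2.** The background safety summary of Study D4190C00006 (Section 3.0) reports treatment-related Grade 3 or worse diarrhea in 7.8% of 102 patients.

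- Count: 8/102 = 7.84%. Seven would give 6.9% and nine 8.8%, so the count is 8.
- Expected in 40: 40 × 8/102 = 3.14.
- Exact (Clopper-Pearson) 95% CI for 8/102: 3.45% to 14.87%. Times 40: 1.38 to 5.95.
- Nausea, vomiting and constipation are absent from that summary's list of Grade 3 or worse events at 5% or more. Each is therefore at most 5/102 = 4.9%, or 40 × 5/102 = 1.96 of 40.

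**Sizing Arm 1.** The summary of Study CD-ON-durvalumab-1108 (694 patients, Section 3.0) lists treatment-related Grade 3 or worse events seen in 3 or more patients.

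- Diarrhea is not on that list, so at most 2. It is named among Grade 4 events, so at least 1. Expected in 40: 40 × 1/694 = 0.06 to 40 × 2/694 = 0.12.
- Vomiting: 3/694. Expected in 40: 40 × 3/694 = 0.17.
- Nausea and constipation are not listed, so each is at most 2/694, or 0.12 of 40.

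**Direction of error.** The Arm 2 figure is probably too high for this trial. The 102 patients include cohorts given tremelimumab 3 and 10 mg/kg, and Section 3.0 says the 20 + 1 mg/kg cohort, the basis for the fixed doses here, had the fewest Grade 3 or worse events. The share of events lasting at least 24 hours despite optimal care is not given and would lower the counts further. In the other direction, these rates cover treatment-related events only, while Section 11.3 is not limited to them.

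**The case against.** The strongest reply is that the tables plainly govern and Section 11.3 is leftover boilerplate. Section 11.1 sends either drug to Table 4 and says combination patients have both agents held or discontinued under Tables 4-6. Section 11.4.3 sends tremelimumab patients with diarrhea or colitis to Table 4. Most of the 3.1 patients sized above are therefore already routed, and an impossible instruction produces a query sooner than a wrong dose. Section 11.1 also calls its instructions guidelines, so following Table 4 may not count as a deviation.

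Much of this stands, and it limits the harm. It does not remove the conflict. Section 11.3 uses mandatory wording, and nothing ranks it below the tables. The routing in Section 11.4.3 covers diarrhea and colitis on tremelimumab only; it does not cover nausea, vomiting or constipation, or diarrhea on durvalumab alone. The guidelines sentence itself refers to reduction instructions, so it adds to the inconsistency.

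One could also read Section 11.3 as meant for non-immune events. It does not say so, and Table 6 conflicts with it there too.

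The background lists of Grade 4 and 5 events do not name diarrhea, which suggests that the 8 Arm 2 cases were Grade 3. But the Grade 4 list looks incomplete: it omits a Grade 4 lipase elevation reported among the dose-limiting toxicities of the same study. The inference about grade is therefore weak. The conclusion does not depend on it, because Table 4 stops combination treatment at Grade 3 and at Grade 4.

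**Conclusion.** The concern holds. Section 11.3 contains an operative safety rule that another section prohibits and the dosing plan makes impossible. If its intent were followed, it would lead to re-treatment where Table 4 or Table 6 requires stopping. The tables are clearly meant to apply in both arms; what is missing is a sentence that removes or overrides the rule.

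The reach is small: roughly 1 to 6 combination patients with qualifying-grade diarrhea, probably fewer, and well under one durvalumab-alone patient for each symptom. This assumes that rates from the earlier studies carry over to endometrial cancer. Sample size, error rates and the ORR and PFS decision rules are not affected. The point should be fixed because it concerns safety conduct and the correction is simple.

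**What to change.** Delete the dose-reduction sentence in Section 11.3 and put in its place: *Manage per Tables 4-6, which govern in both arms; dose reductions are not permitted.* In the opening sentence of Section 11.1, remove the words *and reduction*.

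The cost is a protocol amendment to two sentences, with no new procedures, visits or patients.

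Two nearby items could be tidied in the same amendment, although this point does not depend on them. One is the table numbers cited in Section 11.1. The other is the 28-day boundary: Section 11.1 takes patients off study once 28 consecutive days are missed, while the second rule in Section 11.3 allows a delay of up to 28 days. That second rule could also be checked against the 14-day limit for Grade 3 events in Table 6.

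### Section 11.3 contradicts the rest of section 11: it orders a dose reduction that is not permitted, and it only delays drug for some events that Tables 4 and 6 stop

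*Combined protocol and SAP*

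**What the plan says.** Section 11.3 (General) has two dose-modification paragraphs.

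- **Gastrointestinal.** Patients whose nausea, emesis, constipation or diarrhea stays at Grade 3 or higher for at least 24 hours despite optimal management "require reduction of one dose level and delay in subsequent therapy for a maximum of 2 weeks until recovered to Grade 1".
- **Organ toxicity.** "Other non-hematologic toxicities with an impact on organ function of Grade ≥ 2 require delay in subsequent therapy for a maximum of 28 days", ending at recovery to Grade 1 or the pre-treatment level. No upper grade is given and no table is cited.

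Section 11.1 says "Dose reductions are not permitted". It also sets its own time limits for drug-related toxicity: "Patients may temporarily suspend dosing of study drug for up to 14 days" and "Patients who miss ≥ 28 consecutive days of scheduled study treatment because of drug-related AEs will be discontinued from the study", with exceptions on approval by the Principal Investigator.

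The detailed rules are in Table 4 (immune-mediated reactions), Table 5 (infusion reactions) and Table 6 (non-immune reactions).

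Some text in section 11.1 softens the conflict. The instructions "are intended to serve as guidelines to allow ongoing treatment", and "there are certain circumstances in which durvalumab or tremelimumab should be permanently discontinued". One sentence sends the reader to Table 4 for modification after the first dose. Another says that rules for immune-mediated reactions, "for infusion-related reactions, and for non-immune-mediated reactions are detailed in Tables 5 and 6", although the immune-mediated rules are in Table 4.

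**The concern.** An investigator who follows 11.3 to the letter meets two problems. The first is an order to lower a dose that another part of the same section says may not be lowered, with no lower level to go to. The second is that, for some serious events, 11.3 describes only a pause until recovery, while the tables end treatment for good.

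What is at stake is patient safety on checkpoint inhibitors and consistent discontinuation decisions across patients and arms. It also becomes unclear which action counts as a protocol deviation.

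**Working it through.** No arithmetic applies. The rules are set side by side, and the events are examples, not a full count.

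| Event | Section 11.3 | Section 11.1 and tables | Result |
|---|---|---|---|
| Persistent Grade 3 or higher nausea, emesis, constipation or diarrhea: dose | Reduce one level | 11.1: no reductions; doses fixed at 1500 mg and 75 mg (section 4.3) | Direct contradiction |
| Grade 3 diarrhea/colitis, combination arm | Reduce, delay up to 2 weeks if persistent diarrhea | Table 4: permanent stop | Conflict |
| Grade 3 diarrhea/colitis, durvalumab alone | Same | Table 4: hold to Grade 1 or lower, resume after steroid taper | Conflict on dose; hold rules differ |
| Grade 4 diarrhea/colitis, either arm | Same | Table 4: permanent stop | Conflict |
| Grade 3-4 pneumonitis, nephritis, neurotoxicity | Delay up to 28 days | Table 4: permanent stop | Conflict |
| Grade 2-4 myocarditis | Delay up to 28 days | Table 4: permanent stop | Conflict |
| Non-immune Grade 3 organ toxicity | Delay up to 28 days, to Grade 1 or baseline | Table 6: resume if Grade 2 or lower within 7 days, or Grade 1 or lower (or baseline) within 14 days; otherwise stop | Differs in both directions |
| Non-immune Grade 4 organ toxicity | Delay up to 28 days | Table 6: stop, with judgment for laboratory values | Conflict |
| Isolated hypothyroidism, Grade 2 or higher | Delay, if counted as organ toxicity | Table 4: replacement therapy without interrupting drug | 11.3 is stricter |

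**Time limits.** Section 11.3 limits the delay of therapy (28 days, or 2 weeks for gastrointestinal events). Section 11.1 limits suspension (14 days) and missed treatment (28 days or more). Table 6 times the recovery of the event (7 or 14 days). These are different quantities, so subtracting one from another would mean nothing. Section 11.1 alone leaves open what happens between a 14-day suspension and 28 missed days.

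**Could 11.3 cover only what the tables leave out?** Table 4 ends with a block for immune-mediated reactions not listed by name, Table 5 takes infusion reactions, and Table 6 takes non-immune reactions at every grade. Almost no treatment-related toxicity remains outside them, and 11.3 does not describe itself as residual.

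**Does any text rank the two?** Section 11.1 points to Table 4 without limit to one arm. For combination patients it says both agents are held or stopped according to Tables 4-6. Table 4 opens by saying modifications will follow severity. Section 11.4.3 sends pneumonitis, diarrhea and colitis under tremelimumab, and endocrine, pancreatic, neurologic and renal events to Table 4. None of these sentences mentions 11.3.

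**The case against.** The strongest reply is that a specific rule prevails over a general one. Section 11.3 is headed General, and its organ-toxicity paragraph names no organ. Table 4 is specific to event and grade. Section 11.1 adds that colitis, pneumonitis, hepatitis, neuropathy, nephritis and similar events without another cause are to be treated as immune-related, which places them in Table 4. The 28-day maximum also fits section 13.0, which lists a delay beyond 28 consecutive days among possible reasons for stopping. An order to reduce a fixed dose is more likely to prompt a query than a lowered dose, and a single-center trial limits variation between sites.

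Much of this stands. For immune-mediated events, investigators would probably follow the tables. It does not remove the conflict. Diarrhea is named in both places with different actions, so general-versus-specific does not settle it cleanly. The diarrhea pointer in section 11.4.3 is confined to tremelimumab, and myocarditis has no pointer there. Calling the text guidance does not reconcile an instruction to reduce with a ban on reducing.

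A reader might infer more, and the documents do not support it:

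- **That 11.3 overrides the tables, or that patients would routinely be re-dosed after, say, Grade 3 pneumonitis.** Section 11.3 does not forbid discontinuation and claims no priority. Section 13.0 stops drug when the investigator or sponsor judges that an event contraindicates further dosing.
- **That 11.3 is always the laxer text.** For resumption after non-immune Grade 3 events and for isolated hypothyroidism it is stricter.
- **That efficacy conclusions are affected.** The decision rules in section 14.0 rest on counts of responders and of progression-free patients in each arm, and their stated error rates do not depend on this text.

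**Conclusion.** Section 11.3 is inconsistent with the rest of section 11. The dose-level reduction is a plain contradiction that cannot be carried out as written. The diarrhea rule conflicts with Table 4 at Grade 3 in the combination arm and at Grade 4 in both arms. The organ-toxicity paragraph conflicts with Tables 4 and 6 for some events, but this part is weaker because other text directs the reader to the tables.

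The finding has no numerical size. The documents do not report how often such events would recover far enough for re-dosing to be considered, so no patient count is given. The view that investigators would probably follow the tables is a judgment about practice, not something the protocol states. The correction should be made because literal reading leaves room to re-dose after events the tables stop. Sample size, power and type I error are untouched.

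**What to change.** Delete the two dose-modification paragraphs of section 11.3, keeping the text on growth factors and blood products. Replace them with a short statement that Tables 4-6 govern holding, resumption and discontinuation in both arms, and that neither drug is dose-reduced.

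In the same edit to section 11.1:

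- Reconcile the 14-day and 28-day limits: say how days are counted, what applies between the two limits, and how they relate to Table 4 holds that last until a steroid taper is complete.
- Correct the reference to Tables 5 and 6 so that it reads Tables 4-6.

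Where the rules differ in substance, the clinical choice belongs to the sponsor and the safety physicians. The cost is a short protocol amendment, with no change to the analysis or the sample size.
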